6 STUDY INTERVENTION

6.1 STUDY INTERVENTION(S) ADMINISTRATION

6.1.1 STUDY INTERVENTION DESCRIPTION

The ARREST study is a pragmatic clinical trial. Other than randomization to one of two arms [**Early ECMO Facilitated Resuscitation Arm** versus **Standard ACLS Resuscitation Arm**] there are no specified study interventions. All surviving patients will have their mRS and CPC score at hospital discharge determined; survival, mRS score, and CPC classification determined at 3 months post hospital discharge; and survival, mRS, and CPC classification determined at 6 months post hospital discharge. Cost per patient, cost per life saved (based on billing charges), safety and ECMO-related complications for the two treatment groups will also be determined.

Screening and Randomization.

There is no recruitment for this study as it is not possible to prospectively identify victims of out-of-hospital cardiac arrest. The subjects will be enrolled under exception from informed consent, 21 CFR 50.24.

EMS providers will deliver standard resuscitation procedures according to their standard practice. If the patient does not have ROSC following 3 defibrillations, EMS providers will call a central dispatch number per standard clinical practice, providing the research team with notification of a potentially eligible ARREST Trial study subject. At the same time the CCL/ECMO team is notified and activated. Immediately following hospital arrival, the research team will evaluate the ARREST Trial inclusion and exclusion criteria and, if eligible, randomize and enter the patient in the study, transferring the patient to the ED or CCL according to group allocation.

No Study Treatment; The following are suggested clinical practices that may or may not occur based on the judgment of the treating physician.

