Standard critical care measures follow guideline statements for post-cardiac arrest care^{13,17,18} and ECMO management¹⁹ with the following additional measures. All patients receive non-contrast computerized tomography (CT) scans of the head, chest, abdomen, and pelvis on CICU admission, assessing for cerebral anoxic injury, trauma, or bleeding. All patients receive therapeutic hypothermia (TH) for 24 hours. Goal temperature is 34° C, but is increased to 35-36° C if significant bleeding has occurred. Patients are maintained in 30-degree reverse trendelenburg with the head midline. Continuous electroencephalogram and near infrared spectroscopy (NIRS; Equanox; Nonin, Plymouth, MN) are initiated within 24 hours. NIRS measures cerebral oximetry and monitors brain perfusion while the patient is on ECMO. Hemodynamics are maintained with mechanical, inotrope, pressor, and vasodilator support to sustain a mean arterial pressure (MAP) between 65 and 100 mmHg. Fluid boluses provide euvolemic fluid status to prevent ECMO circuit chugging. ECMO flow is maximized until pressors are discontinued, then reduced, as tolerated, promoting native cardiac function. ECMO decannulation readiness is assessed daily with short durations of reduced ECMO flow and simultaneous echocardiography. On ECMO, ventilators are kept on rest settings with 7-10 cmH₂O positive end-expiratory pressure at 12 breaths per minute, and a tidal volume of 6-8 mL/kg ideal body weight. Plateau pressures are maintained below 30 cmH₂O. Settings are adjusted after ECMO decannulation. Continuous veno-venous hemodialysis is provided when needed. Potassium is replaced up to 3.0 mmol/L during TH and 4.0 mmol/L once rewarmed. Enteral nutrition is provided via oral-gastric (OG) or nasal-gastric (NG) access once rewarmed. All patients receive five days of empiric, broad-spectrum antibiotics with narrowed coverage thereafter, as necessary. Daily surveillance blood cultures are performed while on ECMO. Blood products are provided with a goal hemoglobin > 8 g/dL, platelets > 100,000 per μ L, and fibrinogen > 200 mg/dL. Heparin maintains an activated clotting time (ACT) of 180-200 sec while on ECMO. For life-threatening bleeding, the ACT goal is reduced as low as 140-160 sec. All PCI patients received aspirin 81mg and ticagrelor by NG or OG tube.⁵⁹

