8.3.3.3 EXPECTEDNESS

Adverse Events Common to Both Treatment Arms due to CPR and prolonged ischemic times

1. Infection/sepsis (Infection: any infection requiring intervention by the treating clinicians; Sepsis: systemic inflammatory response syndrome in response to an infectious process (confirmed by the treating clinicians))

2. Acute kidney injury (AKI) (Confirmed by the treating clinicians). (Increase in serum creatinine ≥ 0.3 mg/dl (≥ 26.5 $\mu\text{mol/l}$) within 48 hours, or increase in serum creatinine ≥ 1.5 times baseline, or Urine volume < 0.5 ml/kg/h for 6 hours, or Urine volume < 0.5 ml/kg/h for 6 hours)
3. Liver failure/injury (Rapid development of hepatocellular dysfunction in a patient without known prior liver disease (confirmed by the treating clinicians)
4. Cardiogenic shock (Intervention required to maintain adequate hemodynamics (confirmed by the treating clinicians)
5. Multiple organ dysfunction syndrome (MODS) Two or more organs in which homeostasis cannot be maintained without intervention (confirmed by the treating clinicians)
6. Seizure activity (Documented by EEG or clinical assessment and confirmed by the treating clinicians)
7. Brain death (**Brain Death** (*The Canadian Neurocritical Care Guideline*) defined brain death as the irreversible loss of the capacity for consciousness combined with the irreversible loss of all brainstem functions, including the capacity to breathe. Brain death is equivalent to death of the individual, even though the heart continues to beat and spinal cord functions may persist (Citation in Data Definitions) **Neurological determination of death (NDD)** is the process and procedure for determining brain death. The Canadian medical standard for NDD is reported in and is described for children. **Ancillary Tests:** The demonstration of the absence of intracerebral blood flow is considered the standard as an ancillary test for brain death. Currently validated imaging techniques are cerebral angiography (1) and radionuclide angiography (2. **Apnea Test on ECMO:** The patient should be placed on continuous positive airway pressure (CPAP) while the sweep gas flow rate is set to a maximum of 1.0 liter/minute. If the PaCO₂ does not rise above 60 mmHg or change by 20 mmHg, the sweep flow can be incrementally lowered to as low as 0.1 liter/minute while still maintaining adequate oxygenation in most circumstances.)
8. Recurrent cardiac arrest
9. Survival to hospital discharge with mRS >3

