10. Critical illness myopathy and neuropathy
11. Rib fractures
12. Sternal Fractures
13. Spleen and liver lacerations
14. Aspiration pneumonitis
15. Pneumothorax/hemothorax
16. Retrosternal hematomas

17. Cardiac Contusions

Adverse Events Potentially Related to Reperfusion Strategies

1. Acute myocardial infarction (caused by advanced reperfusion strategies)
2. Acute stroke (caused by advanced reperfusion strategies)
3. Injury to the canalized artery (caused by advanced reperfusion strategies)
4. Pericardial effusion or tamponade (caused by advanced reperfusion strategies)
5. Bleeding requiring transfusion (caused by advanced reperfusion strategies)
6. Acute renal failure (caused by contrast dye)
7. Deep venous or arterial thrombosis/embolism (caused by advanced reperfusion strategies)
8. Pulmonary edema (caused by advanced reperfusion strategies)
9. Hemolysis, acquired von Willebrand factor deficiency, or thrombocytopenia (caused by ECMO)
10. Lower limb ischemia (caused by advanced reperfusion strategies)
11. Mechanical failure of the ECMO device
12. Death (as a direct complication of advanced reperfusion strategies)

ECMO Device-Related Adverse Event

1. Mechanical: Oxygenator failure (*Requiring change due to clot formation or gas exchange failure or blood leak*)
2. Mechanical: Raceway rupture (*(In a roller pump rupture of the raceway tubing)*)
3. Mechanical: Other tubing rupture (*Rupture of ECLS tubing*)
4. Mechanical: Pump Failure (*Requiring hand cranking or pump exchange*)
5. Mechanical: Heat exchanger malfunction (*Malfunction of heat exchanger leading to unintentional hypothermia <35C or hyperthermia >39*)
6. Mechanical: Clots: oxygenator (*Requiring change due to clot formation or gas exchange failure or blood leak*)
7. Mechanical: Clots: bridge (*Requiring change due to clot formation or mechanical failure*)
8. Mechanical: Clots: bladder (*Requiring change due to clot formation or mechanical failure*)

9. Mechanical: Clots: hemofilter (*Clots in hemofilter causing hemofilter to need to be changed or to fail*)
10. Mechanical: Clots: other (*Requiring change due to clot formation or mechanical failure*)
11. Mechanical: Clots: Circuit Component Clots (*Circuit component [e.g. pigtails, connectors, bridge, arterial or venous tubing] requiring change due to clot formation or mechanical failure*)
12. Mechanical: Air in circuit (*Requiring circuit intervention or circuit clamping for bubble detector alarm, visualized air, air entry into patient*)

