38. Cardiovascular: Inotropes on ECLS (Dobutamine. Dopexamine. Epinephrine (adrenaline) Isoprenaline (isoproterenol) Norepinephrine (noradrenaline)

39. Cardiovascular: CPR required (*Chest compressions and cardiopulmonary resuscitation required during ECLS run*)
40. Cardiovascular: Myocardial stun by echo (*Confirmed by the treating clinicians*)
41. Cardiovascular: Cardiac arrhythmia (*Requiring antiarrhythmic medication infusion, overdrive pacing, cardioversion or defibrillation*)
42. Cardiovascular: Hypertension requiring vasodilators (*Confirmed by the treating clinicians*)
43. Cardiovascular: Tamponade (blood): (*Tamponade during ECLS run requiring pericardial drain or mediastinal washout*)
44. Cardiovascular: Tamponade: air (*Confirmed by the treating clinicians*)
45. Cardiovascular: Tamponade (not blood): (*Tamponade during ECLS run requiring pericardial drain or mediastinal washout*)
46. Pulmonary: Pneumothorax requiring treatment (*Requiring insertion of chest drain*)
47. Pulmonary: Pulmonary hemorrhage (*Requiring pRBC transfusion(>3U PRBCS/24 hrs in adults)*)
48. Infectious: Culture proven infection (*Confirmed by the treating clinicians*)
49. Infectious: WBC < 1,500
50. Metabolic: Glucose < 40
51. Metabolic: Glucose > 240
52. Metabolic: pH < 7.20
53. Metabolic: pH > 7.60
54. Metabolic: Hyperbilirubinemia (*total bilirubin >170umol/L (> 10mg/dL) or conjugated bilirubin >51umol/L (>3mg/dL), or need for extracorporeal purification for elevated bilirubin*)
55. Metabolic: Moderate hemolysis (*Peak plasma hemoglobin 50-100 mg/dL or 500-1000 mg/L occurring at least once during ECLS run. Sustained for at least 2 consecutive days*)
56. Metabolic: Severe hemolysis (*Peak plasma hemoglobin > 100mg/dL or >1000 mg/L occurring at least once during ECLS run. Sustained for at least 2 consecutive days*)
57. Limb: Ischemia (*Post peripheral cannulation, requiring addition of limb reperfusion cannula >=6 hrs post cannulation*)
58. Limb: Compartment Syndrome (*Requiring fasciotomy*)

59. Limb: Fasciotomy (*Fasciotomy performed secondary to compartment syndrome from ECLS cannulation [fasciotomy performed during ECLS hospitalization]*)

60. Limb: Amputation (*Limb amputation secondary to complications from ECLS run (amputation performed during ECLS hospitalization)*)

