9.4.4 SAFETY ANALYSES

The incidence of AEs will be recorded for all patients in the safety population and presented by treatment arm to the DSMB for review during the study, as well as summarized and compared across treatment arms in the final report of study results. AEs attributable to advanced reperfusion strategies will be reported separately. The statistical significance of differences in safety signal incidence between the 2 treatment groups will be reported. Emphasis will be placed on the presentation of primary study results, with statistical tests provided for guidance on the precision of estimates as indicated. The DSMB must weigh risks against benefits. Thus, interim presentations to the DSMB will include between-group comparisons of the relation of severe adverse events (including deaths) to favorable outcomes. Similar considerations apply to publication of study results when the trial is completed. The specific adverse events listed that potentially reflect the safety of the Early ECMO Facilitated Resuscitation may or may not affect survival to hospital discharge or longer term functional outcome.

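### CPR injuries are sought by CT only in patients who reach the CICU, and surveillance cultures are tied to ECMO, yet Section 9.4.4 tests safety incidence between arms with no allowance for unequal detection

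*Combined protocol and SAP*

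**What the plan says.** The post-resuscitation pathway in Section 6.1.1 sets out two procedures that find events. On imaging: "All patients receive non-contrast computerized tomography (CT) scans of the head, chest, abdomen, and pelvis on CICU admission". On infection: "Daily surveillance blood cultures are performed while on ECMO". The section opens its description of care with the caveat "The following are suggested clinical practices that may or may not occur based on the judgment of the treating physician". Under its standard ACLS paragraph, a patient without ROSC may be declared dead in the ED once a minimum period has passed.

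Section 8.3.3.3 has a list headed "Adverse Events Common to Both Treatment Arms due to CPR and prolonged ischemic times". It contains infection/sepsis and the CPR injuries: rib and sternal fractures, "Spleen and liver lacerations", pneumothorax/haemothorax, retrosternal haematoma and cardiac contusion. Infection is defined there as "Infection: any infection requiring intervention by the treating clinicians". A culture-based item, "Infectious: Culture proven infection", stands on the separate ECMO device list.

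Section 8.2 makes serious adverse events common to the two groups a safety outcome. Section 9.4.4 then says: "The statistical significance of differences in safety signal incidence between the 2 treatment groups will be reported". It refers to a safety population that Section 9.3 does not define. It speaks of AEs, whereas Section 8.3.5 limits tracking to SAEs and Section 8.3.4 to events that start after enrolment.

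**The concern.** Whether a CPR injury enters the record depends on whether the patient lives long enough to be scanned, and treatment assignment is expected to change that. A patient who dies in the ED may have the same fractures as one who is admitted, but no planned procedure looks for them. Compressions begin before randomisation in both arms, so much of this injury cannot be an effect of assignment.

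For infection, the intensity of looking follows ECMO receipt. The early arm is built around ECMO; in the standard arm it is used only in some patients with ROSC.

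No section equalises detection, sets a denominator of patients assessed, or records why a culture was taken. At stake is how the DSMB and the final report read the safety tables. Section 9.4.4 asks the DSMB to weigh risk against benefit, and Section 9.4.1 says the data will inform a decision on a multicentre trial.

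**Working it through.** **The plan's own figure.** Section 9.1 (Operating Characteristics) gives power 0.905, null rejection 0.048 and, under the alternative, a mean of 52.5 ECMO and 29.2 standard patients. Simulating 10,000 trials with its stated rules gives 0.904, 0.046, 53.0 and 29.3. So 52 v 29 is a fair expected size for the safety tables if the design assumptions hold. The documents give no figure for the detection problem itself.

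**CPR injury: inputs.** All of these are assumptions except where a source is given.
- True injury frequency T, equal in both arms: 50%, with 20% as a check.
- Share reaching the CICU, a. Three pairs were tried.
  - 89% v 10-20%: 55/62 = 0.89, from ECMO Exposure in Section 6.1.1, is a proxy only. The standard-arm figure is prompted by ROSC below 10% in Section 2.3.1.
  - 80% v 30%: assumed.
  - 37% v 12%: floors implied by the assumed survival in Section 9.2.
- Share of injuries recorded in unscanned patients, u: 0, 30% or 50%. CT is taken to find every injury.

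Recorded incidence = T × [a + (1 − a) × u]. Example at 80% admission and u = 30%: 0.5 × (0.80 + 0.20 × 0.3) = 43.0%. At 30% admission: 0.5 × (0.30 + 0.70 × 0.3) = 25.5%. The ratio is 1.7.

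The false-significance rate is the exact binomial probability that Fisher's two-sided test gives p < 0.05. Section 9.4.4 names no test; Fisher's is the one Section 9.4.3 names for categorical outcomes.

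| CICU share, early / standard | u | Recorded, early / standard | Ratio | P(p < 0.05), 52 v 29 |
|---|---|---|---|---|
| 89% / 10% | 0 | 44.5% / 5.0% | 8.9 | 0.99 |
| 89% / 20% | 0 | 44.5% / 10.0% | 4.5 | 0.91 |
| 89% / 10% | 30% | 46.2% / 18.5% | 2.5 | 0.67 |
| 89% / 20% | 30% | 46.2% / 22.0% | 2.1 | 0.52 |
| 80% / 30% | 0 | 40.0% / 15.0% | 2.7 | 0.61 |
| 80% / 30% | 30% | 43.0% / 25.5% | 1.7 | 0.28 |
| 37% / 12% | 0 | 18.5% / 6.0% | 3.1 | 0.28 |
| 37% / 12% | 50% | 34.3% / 28.0% | 1.2 | 0.06 |

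At T = 20% and u = 0, 89% v 20% gives 17.8% v 4.0% and a rate of 0.39. At T = 20%, 37% v 12% gives about 0.04 for u of 0 or 50%. Among scanned patients the ratio is 1.0 in every row, because the CT is the same for all of them.

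**Infection.** Assume a 30% true rate among admitted patients, admission of 80% v 30%, and detection of 0.90 on ECMO and 0.60-0.90 off it.
- With equal detection (0.90), the all-randomised comparison is 0.8 × 0.27 = 21.6% against 0.3 × 0.27 = 8.1%, a ratio of 2.7. This excess comes entirely from more patients living to be at risk.
- For surveillance alone, compare admitted patients. Let all early-arm admissions be on ECMO: 0.30 × 0.90 = 27.0%. Let one in six standard-arm admissions be on ECMO, with off-ECMO detection of 0.60: 0.30 × (0.90/6 + 0.60 × 5/6) = 19.5%. The ratio is 1.38. With five in six on ECMO and off-ECMO detection of 0.75 it is 27.0/26.25 = 1.03.
- Even at 1.38, the chance of p < 0.05 among admitted patients is only about 0.05 (arms of 52 and 29) to 0.09 (75 per arm).

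**The case against.** A reader might infer that the plan looks harder in the ECMO arm and will therefore report harm. The documents do not support that. The CT rule is identical for every admitted patient, so the imbalance comes from who reaches the CICU. Cultures follow ECMO receipt, which Sections 4.1 and 6.1.1 allow in both arms, and the pathway is only suggested.

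A reader might also treat false significance as near certain. The 0.91-0.99 rows need three things: 55 of 62 read as CICU admissions, which the text does not say (55 is the balloon-pump denominator); no injury recorded without CT; and a 50% true frequency. The 10% standard-arm admission is also below the 12% survival the design assumes.

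For infection, counting every incidental positive culture as an event would give a large effect. Section 8.3.3.3 requires intervention by clinicians, and Section 8.3.5 limits collection to SAEs. This filter is real but imperfect: all patients already receive empiric antibiotics, and a surveillance positive can prompt the treatment that makes it count.

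Nor does the plan assign an excess of CPR injury to ECMO. Section 8.3.3.3 labels these events as due to CPR and ischaemia, Section 8.3.3.2 requires a relatedness grade, Section 10.1.5 provides adjudication of serious and unexpected events, and Section 9.4.4 offers its tests as guidance. Section 8.3.4 may also exclude injuries that precede enrolment, although the list in Section 8.3.3.3 still includes them.

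Finally, dropping surveillance-detected infections or CT-detected injuries from comparison could hide real harm. That objection stands, and the fix keeps them in view.

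**Conclusion.** The point holds as a detection problem in the planned safety comparison. The direction for CPR injury is likely, provided that more early-arm patients reach the CICU and that the denominator is everyone randomised. The size is not determined by the documents: at 50% true frequency and 52 v 29 patients, the ratio is about 1.2 to 9 and the false-significance rate about 0.06 to 0.99. At lower true frequency the rate can fall to 5% or less. For infection, unequal surveillance adds a factor of about 1.03 to 1.38 under assumed sensitivities; most of any all-randomised excess would come from longer survival. The undefined safety population, and the conflict between AEs in Section 9.4.4 and post-enrolment SAEs in Sections 8.3.4-8.3.5, leave open which of these events will be counted. The change is worth making because it is cheap and stops a detection difference being read as a treatment effect.

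**What to change.** Amend Sections 8.3.3.3 and 9.4.4, with a definition added to Section 9.3.

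1. Report CPR-injury events by arm with the number CT-scanned as denominator, and show unscanned patients as not assessed. State that an all-randomised p-value for these events will not be interpreted as a treatment effect. Keep bleeding or injury that arises or worsens after randomisation in the between-arm safety comparison.
2. Add a CRF field for culture indication (surveillance or clinical). Keep every infection that meets the Section 8.3.3.3 definition in the main comparison. Add a sensitivity comparison limited to clinically detected infections, and list surveillance-only positives by arm and ECMO status.
3. Define the safety population, and reconcile Section 9.4.4 with Sections 8.3.4 and 8.3.5 on AEs against SAEs that start after enrolment.

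The cost is one CRF field and some wording; clinical care is unchanged. The limitation is that the scanned group is selected after randomisation, so the scanned-only figures are descriptive and not a randomised comparison.

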6.2 PREPARATION/HANDLING/STORAGE/ACCOUNTABILITY

6.2.1 ACQUISITION AND ACCOUNTABILITY

All ECMO devices (Cardiohelp, Maquet Rotaflo; Maquet Cardiovascular; Wayne, NJ) will be stored by the perfusionists per standard clinical practice.

6.2.2 PRODUCT STORAGE AND STABILITY

At all times one device will be pre-primed and placed in the CCL to be available for use. The University of Minnesota initiates ~200 ECMOs per year for resuscitation and other indications and the average time from pre-priming to use is 2-3 days.

6.2.3 PREPARATION

Perfusionists perform daily rounds to verify the status of available devices in the CCL as part of their daily workflow. These are not experimental devices and will be managed per standard protocol. Maintenance is based on contractual agreements by the hospital cardiorespiratory division and the company.

6.3 MEASURES TO MINIMIZE BIAS: RANDOMIZATION AND BLINDING

Patients eligible for this study will be VT/VF OHCA patients refractory to standard treatment as defined by the ARREST Trial inclusion and exclusion criteria. Initially patients will be randomly allocated in a 1:1 ratio immediately following hospital arrival. As noted in the Statistical Considerations section, this trial has a Bayesian Adaptive Design, which means that the treatment allocation ratio may be changed later to reduce the probability of assignment to an inferior treatment arm. See Section 9 below. The study has been designed to minimize treatment bias as far as possible. EMS providers will be blinded to the study. University of Minnesota Refractory VF/VT Protocol patients are placed on LUCAS and transferred to the University of Minnesota with ongoing mechanical CPR per standard of care. All out-of-hospital care, including CPR, ACLS, and resuscitation efforts, will be implemented using ACLS guidelines and automated CPR (LUCAS™2) and treatment will be unchanged. Patients will be randomized and entered in the study by research personnel only after hospital arrival and assessment of ARREST Trial inclusion and exclusion criteria. Emergency department personnel will be aware of group assignment. However, ED treatment of all patients follows protocol and standard of care. CCL personnel also will be aware of group assignment, but treatment is similarly protocolized. Post-CCL care in the CICU will be blinded to group assignment. Patients in both groups could have received identical treatment. Patients from both groups will be treated with the same established CICU post arrest protocol by the same critical care team. The PIs will not be involved in any end-of-life decision making. The **Figure** below shows the phases of care in which providers are blinded to group allocation (in light blue).

Thus, we expect patients in both groups to similarly reflect the gender, ethnic diversity, severity or duration of cardiac arrest, and receive the same therapy except early ECMO facilitated resuscitation versus standard ACLS resuscitation.

[figure not shown]

Figure: Patient flow chart showing blinding.

The secondary endpoints (mRS scores and CPC classifications) at hospital discharge, 3 months, and 6 months will be blinded assessments. These will be acquired by someone who is certified in the completion of the mRS and trained and competent to also assess CPC classification (although no certification exists for CPC classification).

Blinded assessment of the mRS and CPC study endpoints will be accomplished as follows:

At hospital discharge, 3 months, and 6 months, a blinded evaluator will determine the mRS and CPC in-person or by telephone. If the patient cannot be evaluated prior to hospital discharge, a blinded evaluator will acquire the mRS score and CPC classification within 2 weeks of hospital discharge by telephone or in-person during a follow up clinic visit.

